Indonesian Hajj Health Officers are health workers assigned by the Minister of Health of the Republic of Indonesia to provide services, guidance, and health protection to pilgrims during the Hajj pilgrimage, not it is only sufficient to have work competence in terms of knowledge, skills and work attitudes that are in accordance with established standards, but it is highly demanded to have excellent physical endurance. An Indonesian Hajj Health Officer is required to have 3 (three) abilities in carrying out his duties and responsibilities in the health sector, namely (a) managerial ability, (b) skill ability and (c) excellent physical ability. Excellent physical ability is one of the main keys to success in providing health services to Indonesian Hajj pilgrims, this is possible because the number of Indonesian Hajj pilgrims is very large and the length of time serving Indonesian Hajj Health Officers for approximately 39 days for TKHI and 76 days for PPIH. The physical fitness of a Hajj Health Officer is required in addition to being in general fitness, they must also be demanded for specific physical fitness. Standardization of individual physical fitness in general can be measured by the $VO_{2\max}$ level is one of the markers of physical fitness and an increase in $VO_{2\max}$. Regular exercise can increase of $VO_{2\max}$ levels. So the higher one's $VO_{2\max}$, also has good endurance. Endurance exercise consists of two groups, namely endurance cardio respiration (general) and muscle endurance (local). For measurement of cardiorespiratory endurance by $VO_{2\max}$. Some of the results of research in the field biomolecular of genetic markers for endurance, one of which is the nrf2 gene, also known as GA-binding protein transcription factor β sub unit (GABPB1), which is a transcription factor in mitochondrial biogenesis. Mitochondrial Biogenesis and nucleus expressed by one of the nrf2 mRNA genes encoded by the GABPB1 gene, located on chromosome 15q212.

2. Objectives

The aim of the research was to examine the effects of Endurance Exercise on the Expression of the mRNA Nrf2 gene and Level of $VO_{2\max}$ of Indonesian Hajj Health Officers.

3. Methods

This study was a single group quasy experiment that took place in two locations the Makassar Health Training Center and Makassar Haji Sudiang Dormitory.

3.1 Participant

Participants are Prospective Indonesian Hajj Health Officers as many as 30 participants consisting of 17 men and 13 women. Criteria for inclusion of participants include: (a) Participants from the Nurse profession aged 30 - 39 years (b) Pass the selection of candidates for Indonesian Hajj Health Officers (c) Understand the physical training program instructions in the rockport method (d) willing to participate in activities and all research provisions . Participants who (a) had a history of coronary heart disease, asthma; (b) not approved by the doctor to participate in the study due to a medical condition, excluded from the study.

3.2 Desain and measure

3.2.1 Exercise Protocol

Subject ($n = 30$), measured $VO_{2\max}$ level 3 times using the Multistage Fitness technique Test (MFT) Bleep Test method (level and feedback) before and after the 1600 meter running exercise duration 20-30 minutes 3 times a week with a frequency of exercise 16 times, then measuring $VO_{2\max}$, 1 week after exercise without running intervention.

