3.3 Statistical Analysis Method

Statistical analysis using SPSS Software (version 21. Inc. Chicago, IL USA) Wilcoxon sign rank test was used to prove the effects of endurance exercise on nrf2 mRNA expression gene and VO_{2max}. Linear regression test and Spearman Rank to analyze the correlation of the nrf2 gene mRNA with VO_{2max} and the Mann Whitney test to prove changes in retention VO_{2max}.

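### Does the running programme (1600 m, 20-30 minutes, 16 sessions at three per week) contradict itself and leave the test dates open?

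*Combined protocol and SAP*

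**What the plan says.** Section 3.2.1 gives the only description of the exercise. VO2max is measured three times: "before and after the 1600 meter running exercise duration 20-30 minutes 3 times a week with a frequency of exercise 16 times", and a third time, "then measuring $VO_{2\max}$, 1 week after exercise without running intervention". The section therefore fixes a distance, a range of minutes, a weekly rate and a total number of sessions. It states no pace, no intensity, no number of weeks and no interval between the last session and the second test.

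Section 3.1 requires participants to "Understand the physical training program instructions in the rockport method". That name is not defined anywhere and does not recur in section 3.2.1.

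Section 3.3 tests the effect of the exercise with a Wilcoxon signed-rank test, so each participant is compared with himself or herself.

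**The concern.** The duration stands directly beside the distance ("1600 meter running exercise duration 20-30 minutes"), so a reader naturally divides one by the other. The resulting speed is low for something called running. A second reader may divide 16 by 3, get a fraction of a week, and conclude that the session count or the weekly rate is wrong and that the later tests have no fixed date. The programme name in section 3.1 suggests that two descriptions of the exercise may be in circulation.

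If the text did conflict, the stakes would be real. The study has one group and one exposure, so its conclusion rests on a before-after change following a known stimulus. One participant might cover a fixed distance at any pace while another exercised for a fixed time over any distance. Both would comply with the text, and the result could not be tied to one defined programme.

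**Working it through.** **Inputs.** Section 3.2.1 gives 1600 m, 20-30 minutes, 3 sessions per week and 16 sessions. It states no speed and no number of weeks, so there is no derived figure of the plan's own to reproduce.

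**Distance against duration, first reading: the minutes are the time for 1600 m.**

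- Speed = distance / time. At 20 minutes: 1.6 / (20/60) = 4.8 km/h, or 20/1.6 = 12.5 min per km.
- At 30 minutes: 1.6 / (30/60) = 3.2 km/h, or 30/1.6 = 18.75 min per km.

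This pace fits badly with the ordinary meaning of running. It conflicts with no other figure, because the documents give no speed.

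**Second reading: the minutes are the length of the session.** No pace follows from the text. To see whether the distance fits, assume running speeds of 6 to 12 km/h (not in the documents):

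- At 6 km/h: 1.6/6 × 60 = 16.0 minutes.
- At 8 km/h: 1.6/8 × 60 = 12.0 minutes.
- At 12 km/h: 1.6/12 × 60 = 8.0 minutes.

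All are below 20 minutes, so distance, duration and running are compatible. Between 20 − 16 = 4 and 30 − 8 = 22 minutes of the session are left undescribed.

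**Sessions against weeks.** 16/3 = 5.33, that is 5 full weeks (15 sessions) and one more. With any fixed set of three training days a week, each session recurs 15 sessions later, on the same weekday five weeks on. Session 16 is therefore 5 × 7 = 35 days after session 1, on day 36 if the first session is day 1. Counting it out for four weekly patterns, each started on any of its three days, gave day 36 in all twelve cases.

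A whole number of weeks would not fix the end date better. Session 15 falls on 28 + 5 = day 33 with training on days 1, 3 and 5 of the week, but on 28 + 3 = day 31 with training on days 1, 2 and 3.

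**Test dates.** The third test is placed one week after exercise. Counted from session 16, that is 36 + 7 = day 43. The interval from session 16 to the second test is not given. It would be equally absent with 15 or 18 sessions, so it has nothing to do with the fraction of a week.

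**Programme name.** Section 3.1 names a method without describing it, and section 3.2.1 describes an exercise without naming it. Nothing in the documents allows the two to be compared, so a conflict cannot be shown from them.

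**The case for a change.** The strongest case for a change is that neither reading gives a complete prescription. If the minutes are the time for the distance, the pace is implausible for running. If they are the session length, up to 22 minutes (on the assumed speeds) are undescribed and no intensity is given. With no comparison group, a loosely described exposure weakens attribution and makes the study hard to replicate. The second test has no stated interval and there is no rule for missed sessions. Eligibility depends on understanding a programme that the exercise section does not name.

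Most of this is true as a description of what is missing. Distance, weekly rate and total sessions are nevertheless stated. The 1.5-fold spread in minutes (30/20) is the range that the protocol itself permits, not an error. Attribution is limited mainly by the absence of a control group, which rewording the session would not cure.

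On timing, if the third test were counted from the second test and not from the last session, the two dates would differ only by the unstated gap between session 16 and the second test. Recording the actual dates shows that gap.

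**Conclusion.** No change to the plan follows. The arithmetic behind the concern is right (3.2 to 4.8 km/h; 5.33 weeks), but it does not show that the plan contradicts itself. The speed depends on one of two readings that the sentence allows, and the other is coherent. The session count and weekly rate together place the last session on day 36, assuming fixed training days and no missed sessions.

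What remains is missing detail: what the minutes cover, the pace or intensity, the interval before the second test, and the link to the programme named in section 3.1. The people running the sessions have to settle these in practice, and the report can state what was done and on which dates. None of them enters the signed-rank comparison as an input, and no stated figure or analysis rule has been shown to give a wrong result. Writing the details down would make the text clearer without altering the analysis. This conclusion takes no position on which exercise dose or schedule is right.

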3.2.2 VO_{2max} Measurement

Level value and feedback from the Bleep test, then the value is converted into the VO_{2max} based on the level achievement and feedback obtained, then the VO_{2max} value is grouped into the form of levels including special, excellent, good, moderate, less and very less.

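### Is VO2max reduced to six fitness grades before it is tested, at a cost in power with 30 participants?

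*Combined protocol and SAP*

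**What the plan says.** Section 3 describes the design: "This study was a single group quasy experiment". Section 3.1 gives the size: "as many as 30 participants consisting of 17 men and 13 women". Section 3.2.1 has VO2max measured three times: before training, after it, and one week later without running.

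Section 3.2.2 has two steps. First, "the value is converted into the VO_{2max} based on the level achievement and feedback obtained". Second, that "value is grouped into the form of levels including special, excellent, good, moderate, less and very less". No cut-points are given for the six grades.

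Section 3.3 names the tests:

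- Training effect: "Wilcoxon sign rank test was used to prove the effects of endurance exercise on nrf2 mRNA expression gene and VO_{2max".
- Association: "Linear regression test and Spearman Rank to analyze the correlation of the nrf2 gene mRNA with VO_{2max".
- Retention: "the Mann Whitney test to prove changes in retention VO_{2max".

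Section 3.3 does not refer to the six grades, and it does not state explicitly that the numeric value is used.

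**The concern.** Grouping is the last step in the only section that defines how VO2max is obtained, and nothing there marks the grades as descriptive. The objective in section 2 speaks of the level of VO2max. Three of the four methods in section 3.3 (Wilcoxon, Spearman, Mann-Whitney) can be run on ordered grades. Read in sequence, the grade could be taken as the form of the outcome that goes to analysis.

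That would matter. A participant whose VO2max rises within a band would count as unchanged. The signed-rank test, as usually run, drops such zero differences and treats every one-band step as equal. Results would then depend partly on how close people start to a cut-point. VO2max is one of two outcomes in the objective, and with 30 participants there is little information to spare.

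**Working it through.** **Step 1: what the plan says is analysed.** Three places bear on this.

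- In section 3.2.2 the term VO2max denotes the converted figure. The grades are a further product made from it. The text says the figure is grouped, not that it is replaced or dropped.
- In section 3.3 every test is attached to VO2max, which is the name of the figure. Linear regression fits a number naturally and a six-category label poorly.
- The same Wilcoxon test is applied in section 3.3 to nrf2 mRNA expression, for which section 3.2.3 describes no grouping. The choice of a rank test therefore does not imply graded data.

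The word *level* does not settle the matter the other way. The introduction uses it for the size of VO2max in general, section 3.2.1 uses it for the measured quantity, and sections 3.2.1 and 3.2.2 also use it for the bleep-test stage.

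**Step 2: what the loss would be if the grades were tested.** The plan gives n = 30 but no SD, correlation, expected gain, significance level, power or cut-points, so there is no figure of its own to reproduce. The following are assumptions: normal values, two-sided 5% significance, five equally spaced cut-points, zero differences dropped.

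The standardised paired change is dz = gain / (SD × √(2(1 − ρ))), where ρ is the within-person correlation.

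- SD 6, ρ = 0.9, gain 1.5: SD of the difference = 6 × √0.2 = 2.68, so dz = 1.5 / 2.68 = 0.56.
- SD 6, ρ = 0.8, gain 2.0: SD of the difference = 6 × √0.4 = 3.79, so dz = 2.0 / 3.79 = 0.53.

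Simulated signed-rank power, 3,000 trials per setting:

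| Setting | Numeric | Six grades |
|---|---|---|
| ρ = 0.9, gain 1.5 | about 82% | 66% / 62% / 50% for bands of 4 / 5 / 7 units |
| ρ = 0.8, gain 2.0 | about 78% | 60–69% across the same bands |

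In the first setting 50–65% of participants are zero differences.

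A second simulation used a wider grid (1,500 trials per setting, bands 0.5 to 1.5 baseline SD wide):

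| ρ | dz | Numeric | Six grades |
|---|---|---|---|
| 0.7 | 0.4 | about 0.54 | 0.34–0.48 |
| 0.7 | 0.55 | about 0.81 | 0.63–0.74 |
| 0.7 | 0.7 | about 0.95 | 0.82–0.92 |
| 0.9 | 0.4 | about 0.54 | 0.22–0.38 |
| 0.9 | 0.55 | about 0.82 | 0.36–0.67 |
| 0.9 | 0.7 | about 0.95 | 0.60–0.86 |

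Setting by setting, the loss is about 3–19 points at ρ = 0.7 and 9–45 points at ρ = 0.9. The two simulations agree: bands of 4 to 7 units at SD 6 are 4/6 = 0.67 to 7/6 = 1.17 SD wide, inside the grid, and dz 0.56 is close to its 0.55 rows.

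**Step 3: the other tests.** For Spearman with a true correlation of 0.4, power is 0.54–0.58 numeric and 0.48–0.57 graded. With 0.5 it is 0.76–0.78 and 0.70–0.77. The loss is about 0–6 points. Retention is assigned to the Mann-Whitney test, which is unpaired and drops no zero differences, so the argument from dropped zeros does not carry over. In simulation, banding made almost no difference to that test. Whether an unpaired test suits repeated measurements is a separate question.

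**Step 4: combine.** All these losses apply only if the grades are tested. If the number is tested, the loss is nil.

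**The case for a change.** The strongest case for a change is that section 3.3 never says which form is analysed, while section 3.2.2 ends with the grades. Two analysts could then read the plan differently, or one could choose after seeing the data. The power at stake in the paired comparison is real under plausible values, one sentence would close the gap, and no new data are needed.

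Part of this stands. The form of the variable is not stated outright, the cut-points are missing, and the conditional power figures reproduce on repetition. It does not stand that the number is lost or that the grades are the planned outcome. That inference rests on a loose word, on the order of two steps in a measurement section, and on rank tests that the plan also applies to an ungrouped quantity. It also has to treat the linear regression as a second mistake, when it is better read as evidence that VO2max is numeric. The power argument bears mainly on the training-effect test: the association test is barely affected, and the retention test does not work by dropping zeros.

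**Conclusion.** The concern does not call for a change. The plan's wording in sections 3.2.2 and 3.3 fits a numeric analysis with the six grades as labels for presentation, and on that reading no power is lost. The loss of 16 to 32 points (82 − 66 and 82 − 50) in the illustrative setting would arise only under the less supported reading. It also depends on an SD of 6, a correlation of 0.9, a gain of 1.5 and bands of 4–7 units, none of which the plan gives. The missing statement of form is a gap that an analyst fills sensibly, because the tests are written for VO2max and the converted figure is available before any grouping.

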3.2.3 Measurement of mRNA NRF2 Gene Expression

RT-PCR analyzes human RNA in the nrf2 RNA sample as the target gene and GAPDH is selected as the housekeeping gene. Samples were preserved in nuclease free water (Norgen biotech, Inc.), and RNA was extracted using the RNA isolation kit "RNAPrep pure kit for blood" (Tiangen Biotech, Beijing). cDNA is cleaned using the "iScript cDNA synthesis kit" (Bio-Rad Laboratories, Inc.) cDNA kit and store at -20°C until analyzed by RT-PCR. RT-PCR is run on CFX96 touch (Bio-Rad Laboratories, Inc.) using the QPCR master mix "Ssofastevagreen supermix" (Bio-Rad Laboratories, Inc.). Specific gene primer pairs are described as follows:

Forward: GAGAGCCCAGTCTTCATTGC;

Reverse NRF2 Primary: TTGGCTTCTGGACTTGGAAC.

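### nrf2 mRNA is referenced to GAPDH alone in a single-group before/after design, so a training-related change in GAPDH would look like an opposite change in nrf2, and nothing in the plan would detect it

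*Combined protocol and SAP*

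**What the plan says.** On the assay, section 3.2.3 states: "RT-PCR analyzes human RNA in the nrf2 RNA sample as the target gene and GAPDH is selected as the housekeeping gene". No other reference gene appears. The primer list holds one pair, ending with "Reverse NRF2 Primary: TTGGCTTCTGGACTTGGAAC". The extraction kit is one for blood. The section gives no normalisation formula, no RNA quantification or fixed RNA input, and no check on GAPDH.

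On the analysis, section 3.3 states: "Wilcoxon sign rank test was used to prove the effects of endurance exercise on nrf2 mRNA expression gene". It adds: "Linear regression test and Spearman Rank to analyze the correlation of the nrf2 gene mRNA with" VO2max. GAPDH is not mentioned there.

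On the design, section 3 (Methods) states: "This study was a single group quasy experiment that took place in two locations". Section 3.1 gives 30 participants. Section 3.2.1 sets the exposure at "3 times a week with a frequency of exercise 16 times", which is 16 / 3 = about 5.3 weeks.

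Two readings here are inferences. That nrf2 is normalised to GAPDH follows from GAPDH's role as housekeeping gene. That blood was taken before and after training follows from the paired test, since the sampling times for nrf2 are not given.

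**The concern.** A housekeeping gene removes differences in RNA input and cDNA yield, which move both transcripts together. It does so validly only if its own abundance per unit of RNA is unaffected by the intervention. With one reference gene, a fall in GAPDH mRNA and a rise in nrf2 mRNA give the same normalised result.

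Three features make this worth checking here. The intervention is an exercise programme and GAPDH encodes an enzyme of glycolysis, so stability ought to be shown. The sample is blood, where a change in the mix of white cells could move either transcript. There is also no control group in which a drift in GAPDH over the same weeks would show or cancel.

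The stake is the molecular half of the objective. A significant signed-rank result would be read as an effect of training on nrf2 when it might come partly or wholly from the denominator.

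**Working it through.** The plan states no SD, effect size, alpha or power for the expression outcome, so there is no figure to reproduce. The check asks how large the consequence would be over a range of assumptions.

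**Inputs from the documents:** n = 30; paired signed-rank test; one reference gene; single group.

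**Assumptions:** PCR efficiency about 100%; two-sided alpha 0.05; normally distributed paired differences; true nrf2 change zero; SD of the within-person change in normalised Ct from 0.5 to 1.5 cycles; mean GAPDH shift of 0.1 to 0.5 cycle.

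**Step 1: size of the error.** The normalised value is Ct(nrf2) − Ct(GAPDH). If GAPDH abundance rises by d cycles (a factor of 2^d), the apparent nrf2 change is 2^−d. If it falls by d, the apparent change is 2^d.

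| d (cycles) | GAPDH rises: apparent nrf2 | GAPDH falls: apparent nrf2 |
|---|---|---|
| 0.10 | ×0.93 | ×1.07 |
| 0.25 | ×0.84 | ×1.19 |
| 0.50 | ×0.71 | ×1.41 |

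**Step 2: false-positive rate of the signed-rank test.** Simulation with n = 30 and 3,000 runs per setting:

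| Mean GAPDH shift | SD 0.5 | SD 0.7 | SD 1.0 | SD 1.5 |
|---|---|---|---|---|
| 0.25 cycle | 74% | 46% | 24% | 14% |
| 0.50 cycle | 100% | 96% | 74% | 42% |

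With no shift the rate was 4% to 6%. Separate runs of 4,000 agreed within about 2 percentage points. They also gave 17%, 8% and 6% for a 0.1-cycle shift at SD 0.5, 1.0 and 1.5.

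A hand check uses the large-sample approximation Φ(d × √(n × 3/π) / SD − 1.96), with √(30 × 3/π) = 5.35. For d = 0.25:

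- SD 0.5: Φ(2.68 − 1.96) = about 76%
- SD 1.0: Φ(1.34 − 1.96) = about 27%
- SD 1.5: Φ(0.89 − 1.96) = about 14%

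**Step 3: the correlation with VO2max.** Suppose GAPDH shifts by the same constant c in everyone. Every normalised Ct at the later time then changes by c, and so does every change score. Ranks are unchanged, so the Spearman coefficient is unchanged. On the log scale the regression intercept moves, but the slope and its p-value do not. On the fold scale every value is multiplied by one constant, so the slope is only rescaled. A numerical check with c = 0.5 cycle gave identical Spearman and log-scale results before and after the shift. Bias would need person-specific GAPDH shifts related to VO2max, or pooling of the time points. Section 3.3 specifies neither.

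**Step 4: what a second reference can do.** Run on the same cDNA, Ct(GAPDH) − Ct(second reference) is free of RNA input, so a paired change in it shows that at least one reference moved. It cannot show which. Normalising to the geometric mean of two references only halves a GAPDH shift: 0.25 cycle becomes 0.125, still 2^0.125 = 1.09-fold.

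**The case against.** The strongest reply is that nothing in the documents shows GAPDH in blood cells changing with training, and that the percentages above are simply the power to detect a bias put in by assumption. That stands. If GAPDH is stable the ratio is valid, and with no shift the test keeps its nominal error. The size of the problem is therefore unknown, but the lack of any means to find out is not.

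A second reply is that some variation in GAPDH is harmless. This also stands. Variation from RNA input or cDNA yield is what normalisation is meant to remove, so only a training-related change in GAPDH mRNA matters.

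A third concerns the obvious free remedy: look at raw GAPDH Ct and require its 95% CI to lie within a margin such as ±0.25 cycle. That gate would be a poor one. The CI half-width at n = 30 is 2.045 × SD / √30, which is 0.19 cycle at SD 0.5, 0.26 at 0.7 and 0.37 at 1.0. With a perfectly stable GAPDH, simulation passes the gate about 51%, 6% and 0.02% of the time respectively (applying those SDs to raw GAPDH Ct is an assumption). Raw Ct is also interpretable only if RNA input was fixed, which section 3.2.3 does not say.

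Finally, a shift in white-cell mix can move nrf2 itself, and no reference gene corrects that. True, and it limits what the fix achieves.

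**Conclusion.** The point holds as a gap in the design. The plan relies on one reference gene, tests only the normalised target in a single group, and has no means of telling a training-related GAPDH change from an nrf2 change. Under an assumed SD of 0.5 to 1.5 cycles, a 0.25-cycle GAPDH shift would raise the false-positive rate of the signed-rank test to between about 74% and 14%, against 5% nominal. Both the SD and the shift are assumptions.

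A reader might infer three stronger things that the documents do not support:

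- That the nrf2 result is biased, or that the trial cannot answer its molecular question. No drift in GAPDH is documented, and if GAPDH is stable the ratio does answer it.
- That the same error carries into the regression and Spearman analyses. A common shift leaves them unchanged within a time point or on change scores.
- That any movement in GAPDH Ct is harmful. Movement due to RNA input or cDNA yield is properly removed.

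**What to change.** **Section 3.2.3.** Run a second, non-glycolytic reference transcript on the same cDNA. State the normalisation formula and the times of blood sampling.

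**Section 3.3.**

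- Report the paired before-to-after change in Ct(GAPDH) − Ct(second reference) with its 95% CI.
- Report the nrf2 signed-rank result against GAPDH, against the second reference, and against their geometric mean.
- Describe the finding as a change in nrf2 mRNA only if direction and conclusion agree across references. Otherwise report it as reference-dependent.
- If RNA input was fixed, tabulate raw GAPDH Ct before and after as a descriptive check, without a pass/fail margin.

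**Cost.** One primer pair and extra wells on existing cDNA, with no new blood draw, visit or staff. The nrf2 result may become less favourable. If the two references disagree, the data will not show which one moved, and a change in white-cell mix that alters nrf2 itself remains uncorrected.
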